6.7.5 Evaluation of Effectiveness

Tumor Response Evaluation

- The assessment of effectiveness is recommended to follow the RECIST v.1.1; however, it is not limited to this method. The choice of assessment method shall be based on the standard procedures of each participating site.
- RECIST v.1.1 provides standardized criteria for assessing changes in tumor burden, including definitions for CR, PR, SD, and PD.
- The guideline is widely used in oncology clinical trials to ensure consistency and comparability of tumor response assessments across studies.
- Whenever possible, the same assessment method should be consistently applied for each individual subject throughout the study period.
- Tumor response, including CR, PR, SD, and PD, and best overall response (BOR) will be assessed by the investigator in accordance with local methods used in routine clinical practice.

⁹ Instrumental ADL refer to preparing meals, shopping for groceries or clothes, using the telephone, managing money, etc.

¹⁰ Self-care ADL refer to bathing, dressing and undressing, feeding self, using the toilet, taking medications, and not bedridden.

6.8 Data Management

The sponsor / program coordinator is responsible for implementing and maintaining a quality management system with written development procedures and functional area standard operating procedures (SOPs) to ensure that this program is conducted, and data are generated, documented, and reported in compliance with the protocol, accepted standards of all applicable laws, rules and regulations relating to the conduct of the study.

Data management will be performed in accordance with applicable MSD/CRO standards and data cleaning procedures to ensure the integrity and accuracy of the data, e.g., removing errors and inconsistencies in the data. MSD may also conduct a quality assurance assessment and/or audit of the site records during the execution period to ensure the integrity and accuracy of the data and the compliance with all applicable regulatory requirements.

All AEs in the (e)CRFs will be classified into the SOC and the PT of AE according to the classification of MedDRA, which is the most current version in use when the summary tabulation is generated.

6.9 Data Analysis and Statistical Analysis

Each endpoint will be analyzed using descriptive statistical methods such as mean, standard deviation, median, interquartile range, and/or minimum/maximum/range for continuous variables. For any categorical variables, frequency and percentage will be reported.

Each evaluation item will be subjected to descriptive statistical analysis in accordance with the statistical analysis plan.

The safety and effectiveness in subjects who are in violation of this protocol including inclusion/exclusion criteria (i.e. protocol violation cases) will be separately presented.

Patient background (age, sex, pregnancy status, lactation status, medical history and comorbidities, prior treatments/concomitant medications, etc.) will be summarized descriptively.

6.9.1 Subject composition

Subject attrition will be reported, including:

- Number of the registered subjects
- Number of the subjects for whom the study form has been collected
- Number of the subjects for whom the study form has been finalized (Number of subjects whom the survey form has been quality checked per 6.5.8)

- Number of the subjects included in safety tabulation/subjects excluded from the tabulation and the reason

The subjects that meet the criteria for safety analysis, are treated with belzutifan at least once, complete at least one follow up visit (e.g., re-visit etc.), and are identified by an investigator whether AE occurred or not will be included in the subjects for the safety evaluation. The ‘safety tabulation’ group will be used for all analyses below unless otherwise noted.

- Number of the subjects included in effectiveness evaluation/subjects excluded from the evaluation and the reason

Only subjects in which a) belzutifan was administered at the recommended dose throughout the observation period or until belzutifan discontinuation and b) have an effectiveness evaluation will be included in the effectiveness analyses.

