5.2 Secondary Objectives

- 1) The overall safety of belzutifan, including safety concerns, in subjects with RCC
- 2) The effectiveness of belzutifan in subjects with RCC

To address the Secondary Objectives, the following points will be addressed:

- a) To describe the patient demographic and baseline clinical characteristics in;
 - In the registered subjects
 - in the safety evaluation group
 - by presence/absence of any AEs
 - by presence/absence of hemorrhage
 - by presence/absence of fracture
 - by presence/absence of anemia
 - by presence/absence of hypoxia.
 - by presence/absence of intracranial lesions
- b) To describe separately the incidence of a) anemia and b) hypoxia, the incidence of AEs including all AEs, ADRs, grade 3-5 AEs, grade 3-5 ADRs, SAEs and SADR
- c) To describe the proportion of subjects of intracranial hemorrhage AEs including all AEs, ADRs, grade 3-5 AEs, grade 3-5 ADRs, SAEs and SADR with or without pre-existing intracranial lesions
- d) To describe the overall incidence and outcomes of AEs, ADRs, grade 3-5 AEs, grade 3-5 ADRs, SAEs, SADR, unexpected SAEs, and unexpected SADR;
- e) For hemorrhage AEs, fracture AEs, anemia AEs, hypoxia AEs, all AEs, All SAEs, All ADRs, all SADR:
 - To describe the proportion of subjects who interrupt drug due and the reasons for drug interruption;
 - To describe the proportion of subjects who discontinue drug and the reasons for drug discontinuation;
 - To describe the proportion of subjects with dose reduction and the reasons for dose reduction;
- f) To describe a) objective response rate (ORR) and b) disease control rate (DCR) in subjects that receive the recommended dose.

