6.3 Planned Subject Number

A sample size of 403 subjects (safety analysis set) is planned to address the objectives of this Study.

This number of subjects was agreed upon with PMDA. This sample size was determined a priori and was not calculated as part of the development of this protocol.

Rationale

In the global Phase 3 clinical study in subjects with advanced RCC MK-6482-005/LITESPARK-005 (Study 005), The incidence of hemorrhage-related adverse events was 12.6% (47/372 subjects), with Grade 3 or higher being 3.8% (14/372 subjects). The incidence of fracture-related adverse events was 4.8% (18/372 subjects), with Grade 3 or higher being 2.2% (8/372 subjects).

To detect 11 or more subjects of Grade 3 or higher hemorrhage-related adverse events, which occurred at an incidence rate of 3.8% in Study 005, with a probability of over 90%, a sample size of 403 subjects is required. Assuming that the incidence of adverse events for the safety evaluation items after marketing is equivalent to that in the 005 trial and setting the number of subjects for safety analysis at 403 it is possible to collect 42 subjects with hemorrhage of which 11 subjects would be anticipated to be Grade 3 or higher; 14 subjects with fractures of which 5 subjects would be anticipated to be Grade 3 or higher; 325 subjects with anemia of which 119 subjects would be anticipated to be Grade 3 or higher; 49 subjects with hypoxia of which 35 subjects would be anticipated to be Grade 3 or higher, with 90% probability under actual usage conditions. Considering dropouts and loss to follow-up, it is thought that registering 410 subjects will ensure 403 subjects for safety analysis. By setting the number of subjects for safety analysis at 403 subjects, it is anticipated to detect the occurrence of hemorrhage, fractures, anemia, and hypoxia under routine clinical practice.

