6.9.3 Secondary Objective analysis

- 1) Patient demographic and clinical characteristics will be analyzed and reported as noted above according to whether they are a categorical or continuous variables for:

- a) the registered subjects
- b) the safety evaluation group
- c) by presence/absence of any adverse event
- d) by presence/absence of hemorrhage
- e) by presence/absence of fracture
- f) by presence/absence of anemia
- g) by presence/absence of hypoxia
- h) by presence/absence of intracranial lesions

- 2) The incidence of anemia AEs and the incidence hypoxia AEs, including all AEs, ADRs, grade 3-5 AEs, grade 3-5 ADRs, SAEs, and SADR will be separately analyzed and reported as categorical variables

- 3) The incidence of intracranial hemorrhage AEs with or without pre-existing intracranial lesions, including all AEs, ADRs, grade 3-5 AEs, grade 3-5 ADRs, SAEs, and SADR reported by the investigator will be separately analyzed and reported as categorical variables
- 4) The incidence of overall safety events reported by investigator, including all AEs, ADRs, grade 3-5 AEs, grade 3-5 ADRs, SAEs, SADR, unexpected SAEs, and unexpected SADR, will be analyzed and reported as categorical variables
- 5) The following will be analyzed and reported as categorical variables for a) hemorrhage AEs, b) fracture AEs, c) anemia AEs, d) hypoxia AEs, e) all AEs, f) all SAEs, g) all ADRs and h) all SADR reported by the investigator:
 - the proportion of subjects who interrupt drug due and the reasons for drug interruption
 - the proportion of subjects who discontinue drug and the reasons for drug discontinuation
 - the proportion of subjects with dose reduction and the reasons for dose reduction
- 6) The following will be analyzed and reported as categorical variables for the effectiveness analysis population based on the investigator's overall assessment after completion of administration, as detailed in the stand-alone statistical analysis plan:
 - ORR: best overall response rate (CR or PR)
 - DCR: best response rate of (CR, PR, SD)

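### The only ORR and DCR planned are computed in a set chosen by events after treatment start, so they describe a selected subset, with bias of unknown direction and size

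*Protocol*

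**What the plan says.** The second secondary objective in Protocol section 5.2 is worded without restriction: "The effectiveness of belzutifan in subjects with RCC". Item f of that section then describes ORR and DCR "in subjects that receive the recommended dose".

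Section 6.9.1 narrows this further. A subject enters the effectiveness analyses only if (a) "belzutifan was administered at the recommended dose throughout the observation period or until belzutifan discontinuation" and (b) they "have an effectiveness evaluation will be included in the effectiveness analyses". Subjects left out are to be counted, with reasons.

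Section 6.9.3, item 6, reports ORR and DCR "for the effectiveness analysis population based on the investigator's overall assessment after completion of administration". It refers to the separate SAP for detail and labels both measures as best response. No other population for ORR or DCR is named.

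Three other places bear on the point:
- Section 6.6 leaves the timing of response assessments to routine care and the method to the site.
- Table 1 in section 6.5 ends effectiveness assessment at progression, other anti-cancer therapy, death or loss to follow-up, and at 52 weeks at the latest.
- Section 6.9.3, item 5, tabulates dose reductions and interruptions as outcomes, so dose changes are expected.

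**The concern.** Neither condition can be known on the day treatment starts.

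Under condition (a), a subject who responds and stays on drug has more time in which to have a dose change and be removed. A subject who progresses early at full dose stays in, because the condition runs only until discontinuation. In the other direction, subjects who tolerate the drug poorly, and may respond less, can also be removed.

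Under condition (b), a subject who dies or is lost before any evaluation leaves the denominator instead of counting as a non-responder.

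At stake is what the ORR and DCR mean. A reader will take them as effectiveness in routine use, as the objective is worded. They will in fact describe subjects who kept to one dose and were evaluated. Section 6.10 discusses selection of sites and non-standard response criteria, but not this selection. The checklist in Annex 1 (item 10.8) says that no sensitivity analyses are described.

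**Working it through.** **What can be reproduced.** The protocol's one sample-size figure concerns the safety set. Section 6.3 asks for at least 11 subjects with Grade 3 or higher hemorrhage at a rate of 3.8%, with probability above 90%. The exact binomial tail is P(X ≥ 11) = 0.8988 at n = 402 and 0.9005 at n = 403, so 403 is confirmed. The allowance from 410 to 403 is 7/410 = 1.7%, also for the safety set. No size is given for the effectiveness set.

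**Where the protocol gives no input.** It states no expected ORR or DCR, no share with a dose change and no share without an evaluation. Everything below is an illustration on assumed values: true ORR 20% and true DCR 60% among all treated subjects.

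**Condition (b) alone.** Let u be the share with no evaluation of any kind, none of whom responded or had disease control. Reported rate = true rate / (1 − u).

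| u | ORR | DCR |
|---|---|---|
| 5% | 0.20/0.95 = 21.1% | 0.60/0.95 = 63.2% |
| 10% | 0.20/0.90 = 22.2% | 0.60/0.90 = 66.7% |
| 20% | 0.20/0.80 = 25.0% | 0.60/0.80 = 75.0% |

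**Condition (a) alone.** Let x be the share dropped for a dose change and r the ORR among those dropped. Reported ORR = (0.20 − x·r) / (1 − x).

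| x | Subjects left of 403 | ORR if r = 10% | ORR if r = 30% |
|---|---|---|---|
| 10% | 363 | 0.19/0.90 = 21.1% | 0.17/0.90 = 18.9% |
| 30% | 282 | 0.17/0.70 = 24.3% | 0.11/0.70 = 15.7% |
| 50% | 202 | 0.15/0.50 = 30.0% | 0.05/0.50 = 10.0% |

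If dropped subjects respond at the same 20%, the ORR is unchanged for any x.

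**Precision.** The 95% half-width at an ORR of 20% is 1.96·√(0.2·0.8/n): 3.9 points at n = 403 and 5.5 points at n = 202.

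**What the toxicity figures do and do not give.** Section 6.3 anticipates "325 subjects with anemia of which 119 subjects would be anticipated to be Grade 3 or higher", that is 119/403 = 29.5%. This is a count to be reached with 90% probability if Study 005 incidence carries over. It is not a dose-change rate: section 6.6 also records transfusion and erythropoiesis-stimulating agents after anemia, and the protocol does not say how many such events lead to a dose change.

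**The case against.** The case for leaving the plan as it is has four parts.

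**The restriction is declared.** Item f of section 5.2 does announce a recommended-dose population. It does not announce that the dose must be kept throughout, or that an evaluation is required; section 6.9.1 adds both. The objection stands for the dose restriction as such, not for those additions.

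**Recommended dose is undefined.** The protocol does not say whether an interruption or a label-directed reduction breaks condition (a). If it does not, condition (a) removes far fewer subjects and the loss of long-treated responders may largely disappear. This stands, and it is why no size can be put on condition (a). It also leaves membership of the set ambiguous.

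**Condition (b) asks for an evaluation, not a scan.** Sections 6.6 and 6.7.5 allow any local method, so clinical progression recorded by the investigator may count. A reader might infer that everyone who deteriorates before imaging is lost. The text supports this only for subjects with no evaluation of any kind.

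**The stakes are limited.** Effectiveness is secondary, all analyses are descriptive, exclusions are counted with reasons, and section 6.10 advises caution. This lowers the weight of the point. Counting exclusions does not, however, correct a percentage computed without them.

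A reader might also infer that subjects still on drug at 52 weeks have no usable response, because item 6 relies on the "overall assessment after completion of administration". The same item names best overall response, section 6.7.5 has the investigator assess it, Table 1 sets the window, and detail is left to the SAP, which is not shown. What remains is wording to reconcile.

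**Conclusion.** The point holds in a limited form. Followed exactly, section 6.9.1 yields a single ORR and DCR in a set selected on tolerance, time on drug and evaluability, narrower than both the objective and item f.

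Condition (b) inflates both rates if subjects without any evaluation are mostly non-responders. Condition (a) can act either way. On the assumed true ORR of 20%, the illustrations run from 21% to 25% for condition (b) and from 10% to 30% for condition (a). These ranges rest entirely on assumed shares.

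Two stronger readings are not supported. A reader might infer that the reported ORR will be too favourable; the net direction is unknown, since condition (a) may lower it. A reader might also infer that at least 30% of subjects will be excluded because of Grade 3 or higher anemia; the 119 of 403 is an anemia count, not a count of dose changes.

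The change is worth making because it is cheap and uses data already collected. It does not touch the primary safety objective.

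**What to change.** 1. Report ORR and DCR mainly in all eligible safety-set subjects, classified at treatment start and regardless of later dose changes. For item f, use those who started at the label-recommended dose. The safety set itself requires one follow-up visit and an adverse-event determination, so it is not purely a baseline set, but the planned allowance is only 7 of 410 registered subjects.
2. Keep subjects without an evaluation in the denominator as non-responders, and show their number.
3. Show the evaluable-only result and the current section 6.9.1 set as supplementary tables. For the latter, state whether interruptions and label-directed reductions break the dose condition.
4. Name this selection in section 6.10.
5. Reconcile the timing phrase in section 6.9.3, item 6, with best overall response and the 52-week window of Table 1 for subjects still on drug.

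**Cost.** Wording in the protocol and SAP and one or two extra tables; the response, dose and date items are already collected under section 6.6. The main ORR may go up or down. Counting unevaluated subjects as non-responders is conservative where a missing evaluation only reflects site practice, which is why the evaluable-only result should stand beside it. The change concerns the analysis set only, not dosing.

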2 STUDY SYNOPSIS

Title	Belzutifan special drug use results survey in radically unresectable or metastatic renal cell carcinoma: a post-authorization safety study (PASS)
Product information	
Therapeutic Category
 
Anticancer drug - Hypoxia-inducible factor 2α inhibitor
 
Active substance
 
belzutifan
 
Brand name
 
WELIREG[®] Tablets 40 mg

Milestones	
Anticipated timeframes for the following major milestones are as follows:
 
Study period
 
MAR 2026 – FEB 2031 (60 months)
 
Registration period
 
APR 2026 – MAR 2029 (36 months)
 
Registration may be discontinued when the target number of cases is reached.
 
Data analysis start
 
MAR 2031
 
Final report
 
MAY 2032 (There are no planned interim reports.)

Rationale and background	
The purpose of this PASS is to comprehensively collect and verify safety information under actual use conditions in domestic subjects based on Japan's GPSP regulations, and to conduct a descriptive investigation. This PASS is being conducted as an additional safety monitoring activity described in the Japanese risk management plan for belzutifan.

Safety Concerns as delineated in the J-RMP for this study
	
Important Identified Risks Anemia and hypoxia
 
Important Potential Risks Hemorrhage and fractures
 
Important Missing Information NA

Objective
	
Among Japanese subjects with radically unresectable or metastatic RCC treated with belzutifan in routine practice,
 
Primary Objective
 
1) To monitor the risk of occurrence of hemorrhages and fractures during the administration of belzutifan in subjects with RCC. In doing so, we will observe the percentage of subjects occurring hemorrhage and fractures during the administration of belzutifan and contrasted the results obtained in this study with the percentage of subjects occurring the relevant AEs observed in the Everolimus group of the Study 005.
 
Secondary Objective
 
1) The overall safety of belzutifan, including safety concerns in subjects with RCC
 
2) The effectiveness of belzutifan in subjects with RCC

Study design
	
Special Survey
 
This study is a non-interventional, descriptive, longitudinal, multi-center collaborative survey.

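### ORR and DCR are planned only in subjects kept at the recommended dose, so the sole effectiveness result describes a subset selected after treatment start and not the subjects named in secondary objective 2

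*Protocol*

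**What the plan says.** The protocol describes the effectiveness population at three widths.

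- **Objective.** Section 5.2, item 2), gives the aim as "The effectiveness of belzutifan in subjects with RCC". The synopsis sets all objectives among Japanese subjects "treated with belzutifan in routine practice". Neither mentions dose.
- **Operational item.** Section 5.2 f) reads "To describe a) objective response rate (ORR) and b) disease control rate (DCR) in subjects that receive the recommended dose". It does not say for how long.
- **Analysis set.** Section 6.9.1 requires that "belzutifan was administered at the recommended dose throughout the observation period or until belzutifan discontinuation". It adds a second condition: only those who also "have an effectiveness evaluation will be included in the effectiveness analyses".

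Section 6.9.3, item 6), computes ORR and DCR "for the effectiveness analysis population based on the investigator's overall assessment after completion of administration". No analysis in all treated or all evaluable subjects is stated. Section 6.9.1 does provide for reporting how many subjects are left out of the effectiveness evaluation, and why. Section 6.10 names unstandardised response assessment as a limitation of the effectiveness data, but not the selection by dose.

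**The concern.** Membership of the set is not known when belzutifan is started. It can take up to 52 weeks to settle (section 6.5.4), and it depends on what happens in that time. Leaving the recommended dose reflects tolerance. It also reflects opportunity, because a subject on drug for a year has longer to need a change than one who stops after a few weeks. The alternative in the rule that ends the condition at discontinuation makes this dependence explicit. Time on drug is plausibly linked to response, so the denominator may be selected by something related to the outcome.

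If the rule stands, the survey's only ORR and DCR could be read as effectiveness in routine use when they describe those who stayed at one dose level for as long as they were treated. Nothing elsewhere repairs this. Section 6.9 presents protocol violations separately, but the protocol does not make a dose reduction in routine care a violation. The tally of exclusions gives counts and reasons, not the responses of those excluded.

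**Working it through.** **1. The plan's own figure.** The protocol gives no expected ORR, DCR or size for the effectiveness set. Its only related figure is the safety set of 403 (section 6.3), sized to see at least 11 Grade 3 or higher hemorrhage cases at a rate of 3.8% with probability above 90%. The exact binomial gives P(X ≥ 11) = 0.9005 at n = 403 and 0.8988 at n = 402, so 403 reproduces. It says nothing about effectiveness.

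**2. Who is kept.** Applying section 6.9.1 to two subjects who both have an evaluation:

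| Course | Condition a) | In the set? |
|---|---|---|
| Progresses and stops early, always at the recommended dose | met until discontinuation | yes |
| Responds, stays on drug, later moves to a dose outside the recommended one | broken at the change | no; the response is removed too |

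**3. Error from the dose condition.** Let f be the share of evaluable subjects excluded for dose. Then

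ORR(all) = (1 − f) × ORR(kept) + f × ORR(excluded),

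so ORR(kept) − ORR(all) = f × [ORR(kept) − ORR(excluded)].

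The document gives neither f nor either ORR, so the following are assumptions shown as ranges. For scale, the number kept is taken from 403.

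| f | Kept of 403 | Error if ORRs differ by 10 points | Error if they differ by 20 points | Possible ORR(all) if ORR(kept) = 25% |
|---|---|---|---|---|
| 10% | 363 | ±1 point | ±2 points | 22.5% to 32.5% |
| 30% | 282 | ±3 points | ±6 points | 17.5% to 47.5% |
| 50% | 202 | ±5 points | ±10 points | 12.5% to 62.5% |

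The last column sets ORR(excluded) to 0% and to 100%. For f = 30%: 0.7 × 25% = 17.5%, and 17.5% + 30% = 47.5%.

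**4. Dependence on the timing of dose changes.** Assume a true ORR of 20%, with responders on drug for 12 months and others for 4. With a constant monthly dose-change rate L,

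ORR(kept) = 0.2·exp(−12L) / [0.2·exp(−12L) + 0.8·exp(−4L)].

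- L = 0.04: 0.1238 / (0.1238 + 0.6817) = 15.4%, with 80.5% kept.
- L = 0.06: 0.0974 / (0.0974 + 0.6293) = 13.4%, with 72.7% kept.

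Section 6.5.4, however, says that most of the adverse events of concern in Study 005 occurred within three months of starting. Suppose a share s of the 12-month cumulative hazard H falls in months 0 to 3 and the rest is spread evenly over months 3 to 12. Subjects on drug for 4 months then carry H × [s + (1 − s)/9]. Solving for H with the same share kept gives:

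| s | ORR(kept), 80.5% kept | ORR(kept), 72.7% kept |
|---|---|---|
| 60% | 18.3% | 17.6% |
| 75% | 19.1% | 18.7% |
| 100% | 20.0% | 20.0% |

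The shortfall from 20% falls from 4.6 to 6.6 points under a constant rate to between 0 and 2.4 points. It would run the other way if subjects who leave the recommended dose respond less often.

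**5. Condition b).** If a share m of subjects has no evaluation and they stay in the denominator, ORR becomes (1 − m) × ORR(evaluable). With an assumed 25% among the evaluable, m = 10% gives 22.5%. The protocol gives no value for m.

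**The case against.** The restriction is deliberate and partly declared, since section 5.2 f) announces a recommended-dose result. Response at the recommended dose is a legitimate quantity when labelled as such. The study is a safety survey in which effectiveness is a descriptive secondary aim with no hypothesis test. Section 6.10 already asks for caution, and counts of exclusions with reasons are planned. The statistical analysis plan, not shown, might add a wider table. All of this stands, and it lowers the weight of the point. It does not remove it: the protocol fixes the population exclusively, section 6.9.1 is stricter than section 5.2 f), and both are narrower than the stated objective.

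Three stronger readings are tempting, and the documents do not support them.

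- **That 30% to 38% of subjects would be lost.** Section 6.3 anticipates "325 subjects with anemia of which 119 subjects would be anticipated to be Grade 3 or higher", and also 35 with Grade 3 or higher hypoxia. With full or no overlap that is 119/403 = 29.5% to 154/403 = 38.2%. Reading this as exclusions assumes that every such event leads to a disqualifying dose change. Section 6.6 also records transfusion, erythropoiesis-stimulating agents and oxygen after these events, and a subject who discontinues at the recommended dose stays in the set. Nor does the rule say that an interruption disqualifies.
- **That ORR would be understated by 5 to 7 points.** That needs a constant dose-change rate, which fits poorly with the early event timing in section 6.5.4.
- **That a planned comparison with trial response rates is spoiled.** The cross-study comparison in section 6.9.4 covers the primary objectives only.

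**Conclusion.** The point holds as a mismatch between the objective and the analysis set, and it should be fixed. The only stated ORR and DCR come from subjects selected by two conditions that are settled after treatment starts, one of them tied to tolerance and time on drug. They do not estimate effectiveness in the subjects named in secondary objective 2, and section 6.10 does not warn of this.

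The size and direction of the error cannot be derived from the protocol. The 1 to 10 points above rest on assumed exclusion shares of 10% to 50% and assumed response differences of 10 to 20 points. The protocol states no dose-reduction rate. It also leaves the recommended dose undefined: if the term covers reduced doses that the label permits, fewer subjects are excluded and the error shrinks. Because effectiveness is secondary and descriptive, this is a correction to make before analysis and does not threaten the study's main purpose.

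**What to change.** - In sections 6.9.1, 5.2 f) and 6.9.3 item 6), report ORR and DCR first in all safety-set subjects, whatever later dose changes they had. Show subjects without an effectiveness evaluation as not evaluable and keep them in the denominator.
- Keep the recommended-dose subset as a labelled supplementary table, and use the same definition of it in sections 5.2 f) and 6.9.1.
- State what the recommended dose covers for that supplementary analysis. This is a definition for tabulation only; it proposes no dose or treatment rule.
- Add the selection to the limitations in section 6.10.

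The cost is a few sentences and one more table. Dosing and tumor response are already collected under section 6.6. The headline figure will mix dose levels, as routine use does, and will be lowered by subjects who are not evaluable. The safety set itself requires a follow-up visit, so a small amount of selection after the start of treatment remains and should be stated.
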